7.1 Sample Size Determination

The power of 60 patients was not determined statistically. The number was determined at the request of the sponsor based on their minimum requirements. In order to compensate for the lack of statistical sample size determination, an increase in alpha and adding an ANCOVA to explain any differences found will be utilized.

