12.1	FUNDING SOURCE	19
12.2	CONFLICT OF INTEREST	19
12.3	DISCLOSURE	20
12.4	SUBJECT STIPENDS OR PAYMENTS.....	20
13	PUBLICATION PLAN	20
14	REFERENCES.....	20
15	ATTACHMENTS	21

CONFIDENTIAL

This material is the property of the Loma Linda University Medical Center. Do not disclose or use except as authorized in writing by the study sponsor

List of Abbreviations

CRF	Case Report Form
FDA	Food and Device Administration
GCP	Good Clinical Practice
IRB	Institutional Review Board
HA	Hydroxyapatite
PLA	Poly-lactic acid
PEG	Polyethylene glycol
CABG	Coronary Artery Bypass Grafting
OR	Operating Room

CONFIDENTIAL

This material is the property of the Loma Linda University Medical Center. Do not disclose or use except as authorized in writing by the study sponsor

Study Summary

Title	Effectiveness of BoneSeal® on sternal bone hemostats in patients undergoing cardiothoracic surgery
Short Title	Effectiveness of BoneSeal®
Protocol Number	Not yet assigned
Methodology	Prospective, randomized, open-label, study design
Study Duration	Estimated duration for the main protocol (start of screening November 2016) to (last subject processed and finishing the study November 2017)
Study Center(s)	Single-center
Objectives	To evaluate the effectiveness of BoneSeal® on bone hemostats in patients undergoing cardiothoracic surgery.
Number of Subjects	60
Diagnosis and Main Inclusion Criteria	Adult patients over 18 years undergoing coronary artery bypass grafting with or without valve replacement or repair ultimately requiring a sternotomy.
Study Product, Dose, Route, Regimen	BoneSeal® Bone Wax Hemostats Dosage regimen is as follows: 1 to 2 units (2.5 or 3.5 grams) per surgery as determined by the surgeon.
Reference therapy	Ostene®
Statistical Methodology	Statistical methods for evaluating postoperative bleeding and need for blood transfusions will include a Fisher's exact test (2 groups, 2 outcomes).

CONFIDENTIAL

This material is the property of the Loma Linda University Medical Center. Do not disclose or use except as authorized in writing by the study sponsor

1 Introduction

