3.2 Primary Study Endpoints

- 1) Qualitative determination of bleeding and hemostatic action during application graded by the surgeon using the mild, moderate, and severe for bleeding and complete, moderate, minimal, and failure for hemostatic action.

CONFIDENTIAL

This material is the property of the Loma Linda University Medical Center. Do not disclose or use except as authorized in writing by the study sponsor

- 2) Occurrence of re-bleeding during the operation will be noted. Reapplication of product will not occur.
- 3) Postoperative hemoglobin as compared to baseline preoperative readings.
- 4) Post-operative chest tube output.
- 5) Intra-operative and post-operative blood product transfusion quantities.
- 6) Sternal wound infection or other complications within 30 days post procedure.

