5.5.4 Return or Destruction of Study Device

At the completion of the study, there will be a final reconciliation of device shipped, device consumed, and device remaining. This reconciliation will be logged on the device reconciliation form, signed and dated. Any discrepancies noted will be investigated, resolved, and documented prior to return or destruction of unused study device. Device destroyed on site will be documented in the study files.

6 Study Procedures

6.1 Study Data Point 1

Hemostasis during surgery will be determined by surgeon's qualitative evaluation. Notation of re-bleed will be made. Re-application of product will not occur.

6.2 Study Data Point 2

Postoperative bleeding will be evaluated by documentation surgical site drainage and the use of blood products.

6.3 Study Data Point 3

30 day post-op follow-up to all for sufficient time to heal and evaluate for possible post-operative infection or complications. This evaluation can be conducted either in person or by phone.

CONFIDENTIAL

This material is the property of the Loma Linda University Medical Center. Do not disclose or use except as authorized in writing by the study sponsor

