7.2 Statistical Methods

Descriptive statistics for mean homeostasis scores, the length of operation time, the surgical drainage output, and the ease of BoneSeal® application.

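### Section 7.1 offers an unquantified increase in alpha as compensation for an uncalculated N of 60; with no alpha stated and six unranked primaries, the false-positive rate is not fixed in advance

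*Combined protocol and SAP*

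**What the plan says.** On the sample size, section 7.1 states that 60 was not determined statistically and adds: "The number was determined at the request of the sponsor based on their minimum requirements". The remedy follows: "In order to compensate for the lack of statistical sample size determination, an increase in alpha and adding an ANCOVA to explain any differences found". Neither the starting alpha nor the raised alpha is given, there or elsewhere. Sidedness is not stated. The ANCOVA has no named outcome or covariate.

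Section 3.2 numbers six primary endpoints without ranking them or giving a success rule or multiplicity rule. They range from surgeon grading and re-bleeding to "Postoperative hemoglobin as compared to baseline preoperative readings", chest tube output, "Intra-operative and post-operative blood product transfusion quantities" and "Sternal wound infection or other complications within 30 days post procedure". Item 1 holds two grading scales and item 5 two periods.

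The Study Summary names the one test attached to outcomes: "Statistical methods for evaluating postoperative bleeding and need for blood transfusions will include a" Fisher's exact test, described as two groups and two outcomes. Section 7.2 is descriptive only: "Descriptive statistics for mean homeostasis scores, the length of operation time, the surgical drainage output" and ease of application. Section 6.2 says "Postoperative bleeding will be evaluated by documentation surgical site drainage and the use of blood products", and no rule turns drainage into the yes/no categories that Fisher's test needs.

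**The concern.** An N chosen on practical grounds is not an error in itself. The error is to present a looser significance threshold as a substitute for sample size justification. Sixty patients carry the same information at any alpha; a higher alpha only moves the trade-off between missed effects and false claims.

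The plan commits to that move without saying how far it goes. It also does not say which primary endpoints will be tested, or which result would count as a finding. A reader of a reported significant difference between BoneSeal and Ostene could not tell what error rate lay behind it, and both the level and the outcome could be settled after the data were seen. The ANCOVA adds to this, because its stated purpose is to account for differences once found rather than to estimate a planned contrast.

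**Working it through.** **Inputs.** From the documents: N = 60 (7.1), six numbered primaries (3.2) and Fisher's exact test for postoperative bleeding and need for transfusion (Study Summary). Not in the documents, so assumed: 1:1 allocation (30 per arm), two-sided tests, nominal alpha of 0.05, 0.10 or 0.20, and event rates mainly 20-50%.

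**1. Can the plan's own figure be reproduced?** No. The 60 is declared non-statistical, and alpha, power, effect size, SD and event rates are all absent. What follows is illustration over a range.

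**2. What raising alpha buys.** Two-sample t-test, true difference 0.5 SD, 58 degrees of freedom, noncentrality 0.5 × √(30/2) = 1.94:
- alpha 0.05: power 47.8%
- alpha 0.10: power 60.6%

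The gain is 60.6 − 47.8 = 12.8 points, bought by doubling the nominal error rate. With ANCOVA at an assumed covariate correlation r (SD multiplied by √(1 − r²), 57 degrees of freedom):

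| r | alpha 0.05 | alpha 0.10 | gain (points) |
|---|---|---|---|
| 0.3 | 51.4% | 64.1% | 12.7 |
| 0.5 | 59.4% | 71.4% | 12.0 |
| 0.7 | 76.0% | 85.0% | 9.0 |

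The covariate adds real precision. The alpha increase does not.

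**3. False-positive rate of the one named test.** The exact size is the sum of the null binomial probabilities of all 30-versus-30 tables whose two-sided Fisher p-value is at most alpha. For two independent outcomes, the chance of at least one false positive is 1 − (1 − size)².

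| Event rate | 0.05: one / two tests | 0.10: one / two tests | 0.20: one / two tests |
|---|---|---|---|
| 20% | 2.2 / 4.4% | 4.6 / 9.0% | 11.0 / 20.7% |
| 30% | 2.6 / 5.2% | 5.6 / 10.9% | 12.3 / 23.1% |
| 40% | 2.6 / 5.1% | 5.2 / 10.1% | 14.7 / 27.2% |
| 50% | 2.7 / 5.4% | 5.2 / 10.2% | 15.5 / 28.6% |

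The one-test figure also applies to two fully dependent outcomes. At lower event rates the figures fall: two independent tests at 0.20 give 18.1% at a 10% rate and 7.3% at 5%.

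**4. What 60 patients can support at alpha 0.05.** The difference detectable with 80% power is 0.74 SD for one continuous primary, and 0.93 SD at the first Holm step (0.05/6 = 0.0083). The expected 95% confidence interval half-width is 2.00 × √(2/30) = 0.52 SD for a continuous outcome. For a proportion it is 1.96 × √(2p(1 − p)/30), which is 20.2, 23.2 and 25.3 percentage points at p = 20%, 30% and 50%.

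**The case against.** The strongest reply is that the named testing is modest and Fisher's test is conservative. The Study Summary speaks of a single Fisher's test, and its two outcomes may simply be the two categories of a 2×2 table. Even with two tests, section 6.2 evaluates postoperative bleeding partly through blood product use, so the outcomes overlap and independence is the less plausible end. On that reading the true size at nominal 0.10 is 4.6-5.6%, about the conventional level. This stands, and is why the one-test range is given beside the two-test range. It does not settle the matter, because the plan does not say that the level is 0.10.

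It is also fair that a relaxed alpha, stated beforehand with reasons, can be a legitimate choice in a small study, and that it does raise power. The fault lies in the missing number and in calling the increase compensation.

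Two stronger readings are tempting, and the documents support neither:
- **Six tests.** A reader might infer that six primaries mean six tests with success on any one. At full nominal size that would give 14-26% at 0.05 and 25-47% at 0.10 (correlation 0.8 to 0). No passage says that all six will be tested or that one positive result suffices, and section 7.2 is descriptive. These figures are hypothetical and carry no weight here.
- **A rate above 20%.** A reader might infer that alpha 0.20 would push the error rate past 20% in general. That requires two independent outcomes with event rates of 20-50%.

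**Conclusion.** The point holds: as written, section 7.1 raises alpha by an unstated amount for a purpose that alpha cannot serve, and nothing in 3.2, 7.2 or the Study Summary fixes the level or the set of primary tests. The plan's actual false-positive rate cannot be computed.

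With 30 per arm and event rates of 20-50%, the range runs from 2.2% (one Fisher test at nominal 0.05) to 28.6% (two independent tests at 0.20). Most of that spread comes from the alpha that the plan omits. Allocation, event rates, dependence and the candidate alphas are all assumptions. The defect itself rests on none of them, since it is plain from the text. This should be fixed; it does not make N = 60 wrong in itself.

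**What to change.** Choose one route before any data by arm are examined.

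**A. Inferential.**
- In 7.1, delete the increase in alpha as compensation and state two-sided alpha 0.05. If the sponsor keeps a higher level, give the number and rationale in advance and do not tie it to sample size.
- In 3.2, the investigator designates one primary endpoint and the others become secondary with 95% confidence intervals. Alternatively, keep all six under Holm's procedure, with one named measure and test per item.
- Name the same primary test in the Study Summary and 7.2. Use Fisher's test only for outcomes given a written yes/no definition.
- Specify any ANCOVA as a pre-planned analysis of post-operative hemoglobin adjusted for pre-operative hemoglobin, which the schedule in 6.4 already collects.

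**B. Descriptive.** State in the Study Summary, 7.1 and 7.2 that the trial is descriptive, report differences with 95% confidence intervals, and remove the alpha and significance-test wording.

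**Cost.** Wording only, with no extra patients or data. Under A, nominal power is lower than at a relaxed level: for 0.5 SD without ANCOVA, 48% at 0.05 against 61% at 0.10. Holm also raises the detectable difference for a continuous item, as shown above. Under B there is no confirmatory claim, and the intervals will be wide: about ±0.52 SD, or ±20-25 percentage points at event rates of 20-50%.

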7.2 Statistical Methods

Descriptive statistics for mean homeostasis scores, the length of operation time, the surgical drainage output, and the ease of BoneSeal® application.

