3.3 Secondary Study Endpoints

- 1) Ease of use of BoneSeal® compared to Ostene® – graded by primary surgeon using a Likert-scale (ranging from 1 [very easy] to 5 [very difficult]).

4 Subject Selection and Withdrawal

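### Section 7.2 states no BoneSeal-versus-Ostene comparison for ease of use, the only secondary endpoint, and plans a mean of a verbal hemostasis grade that has no numeric codes

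*Combined protocol and SAP*

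**What the plan says.** Section 3.3 lists one secondary endpoint: "Ease of use of BoneSeal® compared to Ostene", scored by the primary surgeon on a Likert scale "ranging from 1 [very easy] to 5 [very difficult". The endpoint is comparative and its numeric codes are given. The Schedule of Events (6.4) records ease of use intra-operatively for the product, without restricting it to one arm.

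The first primary endpoint in Section 3.2 is the surgeon's qualitative grading, "mild, moderate, and severe for bleeding and complete, moderate, minimal, and failure for hemostatic action". These are two separate ordered scales, one of three words and one of four. Neither has numbers.

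Section 7.2 is one sentence. It opens "Descriptive statistics for mean homeostasis scores" (homeostasis is read here as a misprint for hemostasis), adds operation time, and closes "the surgical drainage output, and the ease of BoneSeal" application. It names neither Ostene nor a contrast between arms.

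**The concern.** There are two gaps in the same sentence.

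First, an analyst who follows 7.2 to the letter describes how easy BoneSeal was to apply and stops. The question in 3.3, whether it was easier or harder to use than Ostene, gets no planned answer.

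Second, a mean of words is undefined until someone assigns numbers, and 7.2 does not say whether the score is hemostatic action, bleeding, or a combination. The trial is open-label, and Section 5.5.3 has the investigators told the allocation. Codes chosen after the grades are seen would therefore be chosen by people who know which arm they favour. A mean can also average away outright failures, which a reader of a hemostat trial would want to see separately.

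**Working it through.** **Does another section fill the gap?**

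- Study Summary: Fisher's exact test is named for postoperative bleeding and need for transfusion. It covers neither ease of use nor the intra-operative grades.
- Section 7.1: an ANCOVA is mentioned to explain differences found, with no outcome or covariate named, and an increased alpha with no value.
- Section 2: surgeons will be asked about ease of use; no analysis is given.
- Section 7.3: the population is all randomized subjects; no analysis is given.

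None states an ease-of-use comparison or a coding. The plan has no figure of its own to reproduce here: Section 7.1 says the 60 patients were not derived statistically.

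**Effect of the codes when distributions cross.** The allocation ratio is not stated, so 30 per arm is assumed. The counts are also assumed, in the order complete/moderate/minimal/failure: arm A 24/0/0/6, arm B 15/12/3/0. Mean = sum of (count × code) / 30, higher being better.

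| Codes | Arm A | Arm B | Reading |
|---|---|---|---|
| 4, 3, 2, 1 | (96 + 6)/30 = 3.4 | (60 + 36 + 6)/30 = 3.4 | tie |
| 4, 2, 1, 0 | (96 + 0)/30 = 3.2 | (60 + 24 + 3)/30 = 2.9 | A ahead |
| 3, 2, 1, −1 | (72 − 6)/30 = 2.2 | (45 + 24 + 3)/30 = 2.4 | B ahead |

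All three codings keep the order of the words. Failure is 6/30 = 20% vs 0/30 = 0% in every row, and complete is 24/30 = 80% vs 15/30 = 50%.

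**Effect when distributions do not cross.** Assumed counts 18/8/3/1 vs 12/10/5/3, so the first arm is better at every cut-point. Higher is now worse.

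- Codes 0, 1, 2, 3: (8 + 6 + 3)/30 − (10 + 10 + 9)/30 = 17/30 − 29/30 = −0.40.
- Codes 0, 1, 3, 9: (8 + 9 + 9)/30 − (10 + 15 + 27)/30 = 26/30 − 52/30 = −0.87.

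The sign is stable, but the size more than doubles.

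**Does a rank method cure hidden failures?** For the crossing example, the probability that A is better plus half the probability of a tie is 0.8 × (0.5 + 0.5 × 0.5) + 0.2 × 0 = 0.60, with Wilcoxon p = 0.12. It needs no spacing between codes, but it leans toward the arm with six failures. Only the category counts and proportions show them.

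**Is an ease-of-use comparison worth having at N = 60?** The 95% CI half-width for a mean difference is 1.96 × SD × √(2/30). For assumed SDs of 0.8, 1.0 and 1.2 Likert points it is about 0.40, 0.51 and 0.61 points on a scale from 1 to 5. That is informative.

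**The case against.** A reader might infer that the plan deliberately drops the Ostene arm, or that 7.2 flatly contradicts 3.3. The documents do not support that. Section 7.2 is a verbless fragment that mentions arms for no item. The endpoint in 3.3 is plainly comparative, the schedule collects ease of use for whichever product is used, and 7.1 anticipates differences being found. Loose drafting is at least as likely as intent. What stands is that no section states the comparison.

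A reader might also infer that the hemostasis result will turn on arbitrary codes whatever the data. That is too strong. The direction changes only if the distributions cross, and the illustration was built to cross. Otherwise the codes change the size of the difference and not its sign. Nor does the coding problem reach ease of use, whose 1-to-5 values are stated.

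It is also fair to object that moving to a rank test does not by itself protect against masked failures, as the 0.60 above shows, and that stratifying by surgeon would rest on surgeon identity and numbers that the documents do not give. Both objections stand, and the fix allows for them.

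Finally, 7.2 gives no between-arm comparison for any outcome, so this is part of a wider gap. It still merits its own correction, because it concerns the only secondary endpoint and the first-listed primary one.

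**Conclusion.** The point holds in this form: 7.2, read literally, describes ease of use for BoneSeal only and states no comparison with Ostene; and it plans a mean of a grade that is neither identified nor coded. The gap is in the analysis plan, not in data collection.

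For hemostasis, the size of a mean difference depends on the codes (−0.40 to −0.87 in the ordered illustration), and its direction can too if the arms cross (tie, A ahead or B ahead). These sizes rest on assumed counts and an assumed 30 per arm; they show what can happen and do not predict this trial's data. The ease-of-use precision also rests on assumed SDs. The change should be made: it affects a listed primary and the only secondary endpoint and costs almost nothing.

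**What to change.** In Section 7.2:

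1. Replace the ease-of-use item with ease of use of each product, compared between arms.
2. Replace the mean hemostasis score with category counts by arm for both surgeon grades, bleeding and hemostatic action. For hemostatic action, add the between-arm differences in the proportions *complete* and *failure*, each with a 95% CI.
3. Compare ease of use and each grade between arms by an ordinal method, for example a Wilcoxon rank-sum test with an effect estimate and 95% CI. State that it is read alongside the proportions, because a rank test alone can also mask failures.
4. If a mean is kept, name the grade it summarises and fix the numeric codes before any data are seen.

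Add surgeon stratification only if surgeon identity is recorded and the numbers allow it.

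The cost is a few sentences. The surgeon grades and the ease-of-use score are already planned in Sections 3.2, 3.3 and 6.4, so no new procedure or patient is needed.

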7.3 Subject Population(s) for Analysis

- All-randomized population: Any subject randomized into the study, regardless of whether they received study device

8 Safety and Adverse Events

8.1 Definitions

Unanticipated Problems Involving Risk to Subjects or Others

CONFIDENTIAL

This material is the property of the Loma Linda University Medical Center. Do not disclose or use except as authorized in writing by the study sponsor

Any incident, experience, or outcome that meets all of the following criteria:

- Unexpected in nature, severity, or frequency (i.e. not described in study-related documents such as the IRB-approved protocol or consent form, the investigators brochure, etc)
- Related or possibly related to participation in the research (i.e. possibly related means there is a reasonable possibility that the incident experience, or outcome may have been caused by the procedures involved in the research)
- Suggests that the research places subjects or others at greater risk of harm (including physical, psychological, economic, or social harm).

Adverse Event

An **adverse event** (AE) is any symptom, sign, illness or experience that develops or worsens in severity during the course of the study. Intercurrent illnesses or injuries should be regarded as adverse events. Abnormal results of diagnostic procedures are considered to be adverse events if the abnormality:

- results in study withdrawal
- is associated with a serious adverse event
- is associated with clinical signs or symptoms
- leads to additional treatment or to further diagnostic tests
- is considered by the investigator to be of clinical significance

Serious Adverse Event

Adverse events are classified as serious or non-serious. A **serious adverse event** is any AE that is:

- fatal
- life-threatening
- requires or prolongs hospital stay
- results in persistent or significant disability or incapacity
- a congenital anomaly or birth defect
- an important medical event

Important medical events are those that may not be immediately life threatening, but are clearly of major clinical significance. They may jeopardize the subject, and may require intervention to prevent one of the other serious outcomes noted above. For example, device overdose or abuse, a seizure that did not result in in-patient hospitalization or intensive treatment of bronchospasm in an emergency department would typically be considered serious.

All adverse events that do not meet any of the criteria for serious should be regarded as **non-serious adverse events**.

Adverse Event Reporting Period

CONFIDENTIAL

This material is the property of the Loma Linda University Medical Center. Do not disclose or use except as authorized in writing by the study sponsor

The study period during which adverse events must be reported is normally defined as the period from the initiation of any study procedures to the end of the study treatment follow-up. For this study, the study treatment follow-up is defined as 30 days following the 30 day follow-up.

Preexisting Condition

A preexisting condition is one that is present at the start of the study. A preexisting condition should be recorded as an adverse event if the frequency, intensity, or the character of the condition worsens during the study period.

General Physical Examination Findings

At screening, any clinically significant abnormality should be recorded as a preexisting condition. At the end of the study, any new clinically significant findings/abnormalities that meet the definition of an adverse event must also be recorded and documented as an adverse event.

Post-study Adverse Event

All unresolved adverse events should be followed by the investigator until the events are resolved, the subject is lost to follow-up, or the adverse event is otherwise explained. At the last scheduled visit, the investigator should instruct each subject to report any subsequent event(s) that the subject, or the subject's personal physician, believes might reasonably be related to participation in this study. The investigator should notify the study sponsor of any death or adverse event occurring at any time after a subject has discontinued or terminated study participation that may reasonably be related to this study. The sponsor should also be notified if the investigator should become aware of the development of cancer or of a congenital anomaly in a subsequently conceived offspring of a subject that has participated in this study.

Abnormal Laboratory Values

A clinical laboratory abnormality should be documented as an adverse event if any one of the following conditions is met:

- The laboratory abnormality is not otherwise refuted by a repeat test to confirm the abnormality
- The abnormality suggests a disease and/or organ toxicity
- The abnormality is of a degree that requires active management; e.g. change of dose, discontinuation of the device, more frequent follow-up assessments, further diagnostic investigation, etc.

Hospitalization, Prolonged Hospitalization or Surgery

Any adverse event that results in hospitalization or prolonged hospitalization should be documented and reported as a serious adverse event unless specifically instructed otherwise in this protocol. Any condition responsible for surgery should be documented as an adverse event if the condition meets the criteria for an adverse event.

CONFIDENTIAL

This material is the property of the Loma Linda University Medical Center. Do not disclose or use except as authorized in writing by the study sponsor

Neither the condition, hospitalization, prolonged hospitalization, nor surgery are reported as an adverse event in the following circumstances:

- Hospitalization or prolonged hospitalization for diagnostic or elective surgical procedures for a preexisting condition. Surgery should **not** be reported as an outcome of an adverse event if the purpose of the surgery was elective or diagnostic and the outcome was uneventful.
- Hospitalization or prolonged hospitalization required to allow efficacy measurement for the study.
- Hospitalization or prolonged hospitalization for therapy of the target disease of the study, unless it is a worsening or increase in frequency of hospital admissions as judged by the clinical investigator.

